**Adverse Events**

central laboratory Hgb values will then be evaluated separately to identify increases, so that HemoCue and central laboratory Hgb values are not compared to each other to identify an increase.

For HemoCue Hgb and separately for central laboratory Hgb values, if there is a Hgb value (or daily Hgb average) within the [AE start date – 30 days, AE start date +15 days] window and an earlier Hgb value (or daily Hgb average) that is within the larger [AE start date – 58 days, AE start date + 15 days] window, and the amount of time between the two Hgb values is:

- Between 1 day and 3 weeks, inclusive, then the Hgb values will be compared to determine if there has been a Hgb increase > 2g/dL.
- Between 15 days and 5 weeks, inclusive, then the Hgb values will be compared to determine if there has been a Hgb increase > 4g/dL.

Unscheduled Hgb values will also be used in the assessment of secondary to excessive erythropoiesis following the guidance specified in Section 14.6.3 for unscheduled Hgb values and multiple Hgb values on the same date.

**Pre-defined Lists of AE Preferred Terms Corresponding with Each AESI**Thrombosis and/or tissue ischemia secondary to excessive erythropoiesis

- Narrow SMQ: Embolic and thrombotic events, arterial
- Narrow SMQ: Embolic and thrombotic events, venous
- Narrow SMQ: Embolic and thrombotic events, vessel type unspecified and mixed arterial and venous
- Broad SMQ: Thrombophlebitis
- Additional Preferred Terms:
 


 
○ Vascular access site occlusion
 
○ Vascular access site complication
 
○ Retinal vascular occlusion
 
○ Administration site ischaemia
 
○ Anterior segment ischaemia
 
○ Application site ischaemia
 
○ Biliary ischaemia
 
○ Bone marrow ischaemia
 
○ Brain stem ischaemia
 
○ Catheter site ischaemia
 
○ Cerebellar ischaemia
 
○ Cerebral ischaemia
 
○ ECG signs of myocardial ischaemia
 
○ Gastrointestinal ischaemia
 
○ Graft ischaemia
 
○ Hepatic ischaemia
 
○ Implant site ischaemia
 
○ Infusion site ischaemia
 
○ Injection site ischaemia
 
○ Intestinal ischaemia
 
○ Ischaemia
 
○ Macular ischaemia
 
○ Medical device site ischaemia
 
○ Myocardial ischaemia
 
	
 
○ Stoma site ischaemia
 
○ Subendocardial ischaemia
 
○ Uterine ischaemia
 
○ Vaccination site ischaemia
 
○ Vestibular ischaemia
 
○ Cerebral small vessel ischaemic disease
 
○ Colitis ischaemic
 
○ Delayed ischaemic neurological deficit
 
○ Hypoxic-ischaemic encephalopathy
 
○ Ischaemic cardiomyopathy
 
○ Ischaemic cerebral infarction
 
○ Ischaemic contracture of the left ventricle
 
○ Ischaemic enteritis
 
○ Ischaemic gastritis
 
○ Ischaemic heart disease prophylaxis
 
○ Ischaemic hepatitis
 
○ Ischaemic limb pain
 
○ Ischaemic mitral regurgitation
 
○ Ischaemic nephropathy
 
○ Ischaemic neuropathy
 
○ Ischaemic pancreatitis
 
○ Ischaemic skin ulcer
 
○ Ischaemic stroke
 
○ Necrosis ischaemic
 

--	---

CONFIDENTIAL

204837

**Adverse Events**

- Peripheral ischaemia
- Renal ischaemia
- Retinal ischaemia
- Spinal cord ischaemia
- Ocular ischaemic syndrome
- Optic ischaemic neuropathy
- Reversible ischaemic neurological deficit
- Transient ischaemic attack

Cardiomyopathy

- Narrow SMQ: Cardiomyopathy

Pulmonary artery hypertension

- High Level Term: Pulmonary hypertension
- Additional Preferred Terms:
  - Right ventricular dilatation
  - Right ventricular dysfunction
  - Right ventricular ejection fraction decreased
  - Right ventricular enlargement
  - Right ventricular failure
  - Right ventricular hypertrophy

Cancer-related mortality and tumor progression and recurrence

- Narrow SMQs:
  - Biliary malignant tumours
  - Biliary tumours of unspecified malignancy
  - Breast malignant tumours
  - Breast tumours of unspecified malignancy
  - Liver malignant tumours
  - Liver tumours of unspecified malignancy
  - Malignancy related conditions
  - Haematological malignant tumours
  - Non-haematological malignant tumours
  - Haematological tumours of unspecified malignancy
  - Non-haematological tumours of unspecified malignancy
  - Malignant lymphomas
  - Myelodysplastic syndrome
  - Oropharyngeal neoplasms
  - Ovarian malignant tumours
  - Ovarian tumours of unspecified malignancy
  - Prostate malignant tumours
  - Prostate tumours of unspecified malignancy
  - Tumour lysis syndrome
  - Skin malignant tumours
  - Skin tumours of unspecified malignancy
  - Uterine and fallopian tube malignant tumours
  - Uterine and fallopian tube tumours of unspecified malignancy
- Additional Preferred Terms:
  - Aplastic anaemia
  - Cytopenia
  - Pancytopenia
  - Aplasia pure red cell

Esophageal and gastric erosions

- High Level Terms:
  - Duodenal ulcers and perforation
  - Gastric ulcers and perforation
  - Gastrointestinal ulcers and perforation, site unspecified
  - Oesophageal ulcers and perforation
  - Peptic ulcers and perforation
- Additional Preferred Terms:
  - Haematemesis
  - Gastrointestinal haemorrhage
  - Upper gastrointestinal haemorrhage
  - Helicobacter duodenitis
  - Helicobacter gastritis
  - Melaena

CONFIDENTIAL

204837

Adverse Events

Proliferative retinopathy, macular edema, choroidal neovascularization
 
 
• Broad SMQ: Retinal disorders
 
 
Exacerbation of rheumatoid arthritis
 
 
• High Level Term: Rheumatoid arthropathies
 
• Additional Preferred Terms: 
 
○ Rheumatoid factor increased
 
○ Rheumatoid factor positive
 
○ Rheumatoid factor quantitative increased
 
 
 
 
Worsening of hypertension
 
 
• Narrow SMQ: Hypertension
 

Blood Pressure Events

BP events will be identified during the study via programmatic sweeps of AE and SAE terms entered into the eCRF (using the narrow SMQ for hypertension). AEs identified this way will require an additional BP Exacerbation eCRF page to be completed that characterizes the event as clinically significant and/or symptomatic.
 
In addition, subjects that experience BP values that meet the following criteria at any visit will also be considered to have a BP event and be required to complete the Blood Pressure Exacerbation eCRF page:
 
 
• SBP: an increase from baseline of <math>\geq 25</math> mmHg or SBP <math>\geq 180</math> mmHg
 
• DBP: an increase from baseline of <math>\geq 15</math> mmHg or DBP <math>\geq 110</math> mmHg
 

BP-related SAEs are those SAEs that have been identified via the BP Exacerbation eCRF page.

General Definitions

 
• Post-Randomization last contact date for censoring (subjects not having AE) will be defined as the study completion date.
 

 
• Treatment emergent last contact date for censoring (subjects not having AE) will be defined as follows: 
 
○ 1 day after the last non-zero dose date (last non-zero dose date + 1) for subjects not having treatment emergent AE and continuing on study past (last non-zero dose date + 1)
 
○ Last non-zero dose date for all other subjects
 
 
 


 
• AE Patient Years: (Cumulative total of time to AE for subjects who have the AE + Cumulative total of censoring time for subjects without the AE) / 365.25 
 
○ For treatment emergent AEs, the start date of the patient years value for each subject should be the treatment start date.
 
 
 

CONFIDENTIAL

204837

Adverse Events

 
○ For post-randomization AEs, the start date of the patient years value for each subject should be the randomization date.
 
○ For follow-up AEs, the start date of the patient years value for each subject should be two days after the last non-zero dose date (last non-zero dose date + 2).
 

 
● Incidence Rate (per 100 patient years): <math>(100 * \text{Number of subjects with at least 1 AE}) / \text{AE person years}</math>
 

 
● For the analysis of the time to AE onset/worsening, if the AE onset/worsening date is missing then the time to AE onset/worsening will be counted as 1 day.
 

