
Potential Risk of Clinical Significance	Summary of Data/Rationale for Risk	Mitigation Strategy
	
2013; Ohnhaus, 1989], daprodustat systemic exposure will decrease over time which will result in a lag period before an effect on Hgb is recognized and is of clinical concern.
 
Daprodustat is an inhibitor of CYP2C8: A clinical drug interaction study between 25mg and 100mg daprodustat with a CYP2C8 substrate (pioglitazone) showed that there is no PK interaction at these doses of daprodustat.
 
Daprodustat is a substrate of BCRP: Population PK analysis from Phase 2 studies suggested that while BCRP inhibitors were a covariate for daprodustat CL/F (8.6% lower clearance) the predicted change in exposure was not considered to be of clinical relevance.
 
Daprodustat is an inhibitor of OATP1B1/1B3: A clinical drug interaction study between 25mg and 100mg daprodustat with an OATP1B1/1B3 substrate (rosuvastatin) showed that there is no PK interaction at these doses of daprodustat.
	
period as outlined in the SoA in Section 2.
 
 • Specific guidance for dose adjustment, dose interruption, or discontinuation of daprodustat based on achieved Hgb is provided in Section 7.2 and Section 8.1. • Unblinded monitoring of safety data by an IDMC in-stream throughout the study.
Other		
rhEPO risks (Control)	
See risks outlined in table for daprodustat for excessive erythropoiesis (polycythemia) leading to thrombosis and/or tissue ischemia, death, MI, stroke, heart failure, thromboembolic events, thrombosis of vascular access, and for cancer-related mortality and tumor progression.
 
Uncontrolled hypertension
 
Pure red cell aplasia
	
 • See mitigation strategies outlined in table for daprodustat for excessive erythropoiesis (polycythemia) leading to thrombosis and/or tissue ischemia; death, MI, stroke, heart failure, thromboembolic events, thrombosis of vascular access; and for cancer-related mortality and tumor progression. • Specific eligibility criteria related to current uncontrolled hypertension are outlined in Section 6.2. • Specific eligibility criteria related to personal history of

Potential Risk of Clinical Significance	Summary of Data/Rationale for Risk	Mitigation Strategy
		pure red cell aplasia are outlined in Section 6.2 .

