6.2. Exclusion Criteria

Participants are excluded from the study if any of the following criteria apply at **screening (Week -4)** and **at randomization (Day 1)**, unless otherwise specified:

CKD Related Criteria

1. **Kidney transplant:** Planned living-related or living-unrelated kidney transplant within 52 weeks after randomization (Day 1).

Anemia Related Criteria

2. **Ferritin:** ≤ 100 ng/mL (≤ 100 μ g/L), at screening.
3. **Transferrin saturation (TSAT):** $\leq 20\%$, at screening. If TSAT is 18 to 20%, then a retest using a new blood sample can be obtained within 7 days of the final laboratory report; the final retest value must be $>20\%$ to confirm eligibility.
4. **Aplasias:** History of bone marrow aplasia or pure red cell aplasia.
5. **Other causes of anemia:** Conditions, other than anemia of CKD, which can affect erythropoiesis. A partial list can be found in the Study Reference Manual (SRM).

Cardiovascular Disease

6. **MI or acute coronary syndrome** within 8 weeks prior to screening through to randomization (Day 1).
7. **Stroke or transient ischemic attack** within 8 weeks prior to screening through to randomization (Day 1).
8. **Heart failure (HF)**: Chronic Class IV HF, as defined by the New York Heart Association (NYHA) functional classification system.
9. **Current uncontrolled hypertension** as determined by the investigator that would contraindicate the use of rhEPO.
10. **Bazett's correction of QTc interval (QTcB)** at Day 1: QTcB >500 msec, or QTcB >530 msec in participants with bundle branch block. There is no QTc exclusion for participants with a predominantly ventricular paced rhythm.

Other Medical Conditions

11. **Liver Disease**: presence of any one of the following liver-related laboratory values or conditions, at screening, is exclusionary:

- Alanine transaminase (ALT) >2x upper limit of normal (ULN);
- Bilirubin >1.5x ULN; or

NOTE: Isolated bilirubin >1.5x ULN is acceptable if bilirubin is fractionated and direct bilirubin <35%.

- Current unstable liver or biliary disease per investigator assessment, generally defined by the presence of ascites, encephalopathy, coagulopathy, hypoalbuminaemia, esophageal or gastric varices, persistent jaundice, or cirrhosis.

NOTE: Stable chronic liver disease (including asymptomatic gallstones, chronic hepatitis B or C, or Gilbert's syndrome) are acceptable if participant otherwise meets entry criteria.

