9.2.7. Adverse Events of Special Interest

The investigator or site staff will be responsible for detecting, documenting and reporting any events that may represent the AEs of special interest listed below (using preferred terms):

- Death, myocardial infarction (MI), stroke, heart failure, thromboembolic events, thrombosis of vascular access (see also Section [9.2.5](#))
- Thrombosis and/or tissue ischemia secondary to excessive erythropoiesis
- Cardiomyopathy
- Pulmonary artery hypertension (see also Section [9.2.6](#))
- Cancer-related mortality or tumor progression and recurrence
- Esophageal and gastric erosions
- Proliferative retinopathy, macular edema, choroidal neovascularization
- Exacerbation of rheumatoid arthritis

The results of any investigation should be recorded on the AE or SAE page, as appropriate, and the relevant AE of special interest page of the participant's eCRF.

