### 8.3.1. Analysis of Adverse Event of Special Interest (AESI)

A prespecified list of MedDRA terms will be used to identify AESIs. Changes to the MedDRA dictionary may occur between the start of the study and the time of reporting and/or emerging data from ongoing studies may highlight additional AESIs, therefore the list of terms to be used for each event of interest and the specific events of interest will be based on the safety review team (SRT) agreements in place at the time of reporting. The details of the planned displays are provided in [Appendix 10: List of Data Displays](#).

AESIs are described in Section [14.6.4](#).

Summaries of AESIs will include the number, percentage, and rate per 100 person-years of subjects having at least one occurrence, the number of events, the number of subjects by number of occurrence, the characteristics of the AE (serious, drug-related, etc.), outcome, maximum intensity, time to first onset/worsening, and action taken summarized by treatment group. For each count, a subject will be summarized as follows:

- Serious/drug-related/severe/fatal: If any specific AE falls in the respective category, the subject will be counted in that category.
- Outcome: The subject will be counted within a category if there is at least one specific AE in that category.
- Maximum intensity: The specific AE with the maximum intensity will be counted for this purpose. For example, a subject will be counted in the ‘severe’ category if there is at least one specific AE with severe intensity. A subject will be counted in the ‘moderate’ category if there is at least one specific AE with moderate intensity and there is no specific AE with severe intensity.
- Time to first onset/worsening (days): The earliest of onset dates for the specific AE – treatment start + 1

If the AE onset date/AE worsening and/or resolution date is missing or incomplete in the database for any occurrence of the specific AE, time to first onset/worsening will be left missing for the subject. These summaries of special interest AEs will be provided for those AEs classified as treatment emergent, follow-up, and post-randomization.

The number and percentage of subjects reporting treatment emergent AESI will also be summarized by treatment group and by preferred term.

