**Adverse Events**

- Death, myocardial infarction (MI), stroke, heart failure, thromboembolic events, thrombosis of vascular access
- Thrombosis and/or tissue ischemia secondary to excessive erythropoiesis
- Cardiomyopathy
- Pulmonary artery hypertension
- Cancer-related mortality and tumor progression and recurrence
- Esophageal and gastric erosions
- Proliferative retinopathy, macular edema, choroidal neovascularization
- Exacerbation of rheumatoid arthritis
- Worsening of hypertension

Potential AESIs will be identified through a pre-defined terms of interest process in which pre-defined lists of AE preferred terms corresponding with each AESI will be used to identify events considered to be potential AESIs. Sites will be prompted via query to complete any necessary additional information for these AESIs in the eCRF.

For the category of thrombosis and/or tissue ischemia secondary to excessive erythropoiesis, after the terms of interest list has been applied, the additional Hgb criteria described below will be applied to identify only those events that are considered to be secondary to excessive erythropoiesis as meeting the AESI definition for thrombosis and/or tissue ischemia secondary to excessive erythropoiesis.

Thrombosis and tissue ischemia events will be considered to be secondary to excessive erythropoiesis if during the window of [AE start date – 30 days, AE start date +15 days] any one of the following 3 events occurs:

- Any Hgb value  $\geq$  13 g/dL (measured pre-dialysis)
- Hgb increase  $>$  2 g/dL over 2 weeks (+1 week)
  - Note: for programming purposes, a +1 week window is applied, corresponding to the allowable visit window, to look for increases  $>$  2 g/dL over 3 weeks
- Hgb increase  $>$  4 g/dL over 4 weeks (+1 week)
  - Note: for programming purposes, a +1 week window is applied, corresponding to the allowable visit window, to look for increases  $>$  4 g/dL over 5 weeks.

To identify Hgb increases that meet the increase criterion above, all Hgb values taken within [AE start date – 58 days, AE start date + 15 days] will be identified. This corresponds to identifying Hgb values that occurred 4 weeks before the [AE start date – 30 days, AE start date +15 days] window of interest. HemoCue Hgb and

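### The cancer AESI term list contains four preferred terms that are not malignancies, one of them a listed epoetin risk, and no stated rule removes such cases before the category is counted

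*SAP*

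**What the plan says.** SAP Section 8.3.1 states the method: "A prespecified list of MedDRA terms will be used to identify AESIs". It then summarises each AESI by treatment group as number, percentage and rate per 100 person-years, and adds that the terms used will follow the safety review team's agreements in force at reporting.

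SAP Section 14.6.4.3 gives the lists. The category "Cancer-related mortality and tumor progression and recurrence" is made of 23 narrow standardised MedDRA queries on tumours and malignancy, plus four additional preferred terms: "Aplastic anaemia", cytopenia, "Pancytopenia" and "Aplasia pure red cell".

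The protocol keeps marrow aplasia and cancer apart:

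- Section 9.2.7 names the AESI as "Cancer-related mortality or tumor progression and recurrence" and mentions neither marrow failure nor cytopenia.
- Section 3.3.1, under the risks of the rhEPO control, gives "Pure red cell aplasia" its own line, apart from the cancer risk.
- Section 6.2 has "History of bone marrow aplasia or pure red cell aplasia" as exclusion 4, among the anemia-related criteria. Malignancy is exclusion 13.

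The category feeds Table 3.057 (treatment emergent), Table 3.066 (follow-up), Table 3.075 (post-randomization), the cumulative incidence plot (Figure 3.014, produced only with 20 or more subjects in total) and the dot plot (Figure 3.019). The programming note for the dot plot specifies an unadjusted raw relative risk and asks that the AESI table and plot be consistent within and across studies.

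**The concern.** A reader of the cancer tables will take the count as cancers. If the SAP is followed to the letter, a participant with drug-related pancytopenia or red cell aplasia, and no tumour, is in that count. Cancer is a named potential risk in the protocol's risk table and a reason for stopping study treatment in Protocol Section 8.1, so the by-arm comparison will be looked at closely even though it is descriptive.

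Two features make the category sensitive to a stray case. Cancer events are likely to be few in about 402 participants followed for a year. And with 2:1 allocation, one case in the epoetin arm changes that arm's proportion twice as much as one case changes the daprodustat proportion. Red cell aplasia is also the one term of the four that the protocol ties to the comparator.

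**Working it through.** The documents state no figure on this point, so there is none to reproduce. The check has two parts.

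**Does anything remove a non-malignant case?**

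- *A second filter after the term search.* SAP Section 14.6.4.3 has one, but only for thrombosis and tissue ischemia, where hemoglobin criteria decide whether an event counts. Nothing comparable is given for cancer.
- *Site queries.* The same section calls the listed hits potential AESIs and has sites prompted for further information. No rule says that this information reclassifies an event.
- *Adjudication.* Protocol Section 9.2.5 refers deaths, MI, stroke, hospitalization for heart failure and thromboembolic events to the Clinical Events Committee. Cancer diagnoses are not on the list. SAP Section 8.3 uses investigator-reported details in the AE summaries whatever the adjudication outcome.
- *Are the terms needed to catch blood cancers?* The query list already holds haematological malignant tumours, haematological tumours of unspecified malignancy, malignant lymphomas and myelodysplastic syndrome. A participant with such a report is counted without the four terms. What the four terms add is participants with no malignancy term reported. They can also move a date: time to first onset uses the earliest qualifying event, so a pancytopenia before a true cancer would set the cancer onset.

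On the text, then, these cases stay in the category.

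**How far could one or two cases move the relative risk?**

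Inputs: 268 and 134 are the planned arm sizes (Protocol Section 10.1.1), used in place of the Safety population, whose size is not known in advance. The base of 6 versus 3 cancer cases (2.2% per arm) is an assumption, chosen so that the true relative risk is 1.

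Formula: RR = (a/268)/(b/134), with 95% CI = exp(ln RR ± 1.96·SE) and SE = √(1/a − 1/268 + 1/b − 1/134).

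| Cases added to 6 vs 3 | Daprodustat | Epoetin | RR | 95% CI |
|---|---|---|---|---|
| none | 6/268 | 3/134 | 1.00 | 0.25 to 3.94 |
| one, epoetin | 6/268 | 4/134 | 0.75 | 0.22 to 2.61 |
| two, epoetin | 6/268 | 5/134 | 0.60 | 0.19 to 1.93 |
| one, daprodustat | 7/268 | 3/134 | 1.17 | 0.31 to 4.44 |
| two daprodustat and one epoetin | 8/268 | 4/134 | 1.00 | 0.31 to 3.26 |

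The last row shows arm-neutral cytopenias falling in the 2:1 allocation ratio: the relative risk does not move.

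The result depends on the assumed base. One added epoetin case gives 0.50 from 2 vs 1, 0.67 from 4 vs 2, 0.80 from 8 vs 4 and 0.88 from 14 vs 7. Every interval includes 1.

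Figure 3.014 is not affected at these counts: 9 base cases plus one to three added cases make 10 to 12, below the 20 needed for the plot.

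**The case against.** The strongest reply is that nothing is concealed. Table 3.080 gives treatment-emergent AESIs by preferred term and arm. Tables 3.081, 3.090 and 3.091 give all AEs by preferred term for the treatment-emergent, post-randomization and follow-up periods. A reader could find the four terms and work out what they contribute. This stands: one might infer that the category hides aplasia events, and the documents do not support that. It does not correct the headline count, rate and relative risk, which are the figures most likely to be cited.

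A reader might also infer that the list favours daprodustat. That would follow only if the added cases fell mainly in the epoetin arm. Red cell aplasia is the only term the protocol ties to epoetin, and exclusion 4 makes it less likely. The other three can occur in either arm, and one daprodustat case moves the result the other way. The direction is open.

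Third, the list may be a deliberately sensitive screen. Other AESI lists are broad too: retinal disorders uses a broad query, and a positive rheumatoid factor counts towards rheumatoid arthritis. A cytopenia can be the first sign of a blood cancer. That is a fair reason to look at such cases, but the SAP gives no such reason and no step that separates the screen from the count.

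Finally, the safety review team may revise the terms, and the dot plot note asks for cross-study consistency. The first point offers a route to a fix but leaves the written list as it is. The second is a sound argument against deleting the terms in this study alone.

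**Conclusion.** The point holds as one of labelling and specificity. Under the SAP as written, four non-malignant terms count as cancer in Tables 3.057, 3.066 and 3.075 and in Figure 3.019, and the category is then wider than the AESI named in Protocol Section 9.2.7. This part rests on the text alone.

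The size is not known. The relative risks above rest on assumed cancer counts and on placing one to three cases by hand; no document gives a rate for either kind of event. They show only that, with few cancers, one or two cases can shift the descriptive relative risk visibly, in either direction, and with intervals too wide to support a conclusion about cancer with or without them. The primary hemoglobin test and the principal secondary IV iron test are untouched. The correction is worth making because it is cheap and gives a cancer count that means what its title says.

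**What to change.** Before unblinding, amend SAP Section 14.6.4.3 and the display list in one of two ways.

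1. Keep the programme-wide cancer category, and add next to it a version without the four terms: count, percentage and rate in Tables 3.057, 3.066 and 3.075, and relative risk in Figure 3.019. Report the four terms by arm in a separate row, 'marrow aplasia/cytopenia'. This respects the cross-study consistency note.
2. Or remove the four terms from the cancer list in all programme studies through the safety review team route in SAP Section 8.3.1, with the same separate row.

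Counting the terms as cancer only when a malignancy term is also reported would add nobody, since that participant is already in the category.

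The cost of the first option is one extra row and a second cancer count to explain. The second needs agreement across studies. Neither needs new data.
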